#### Subject Selection

When patients go on-line to investigate the current Zyppah boil and bite design, they will see one of the following buttons on the web page.

Subjects will be recruited online. A total of 500 patients will be recruited to the trial. Even assuming a 30% drop-out rate or failure to complete the study questionnaires, the remaining patients should be sufficient to generate statistically significant data if the device is effective.

#### Gender

No effort will be made to differentiate users based on gender, and there are no gender-specific enrollment restrictions. It is anticipated that the enrollment in the study will reflect the prevalence of the condition in the general population, with men comprising a higher percentage of the study population. Pregnant women will be allowed to enroll in the study, as this is a non-significant risk study and there is no rationale for any additional risk associated with pregnancy.

## Age of Subjects

The only restriction on age is over the age of 18. It is anticipated there will be a broad range of ages represented.

## Racial and Ethnic Enrollment

There are no racial or ethnic limitations on enrollment, and it is anticipated the study population will match the patient population at large. No data will be collected on racial or ethnic identification.

## Inclusion Criteria

- Over 18 years of age
- Living in the United States
- Signing the Informed Consent Form

# Exclusion Criteria

- Missing teeth (as the device won't be properly fitted)
- Any severe breathing or respiratory disorder, such as chronic asthma, emphysema, COPD, or a similar condition
- Poor dental health, such as severe gum disease, loose teeth, an abscess, mouth sores, or bleeding gums
- A dental implant placed within the last three months
- Diagnosed with a Temporomandibular joint condition (TMJ)
- Actively experiencing any mouth or jaw pain, including clenching of the teeth, grinding, or any other physical injury to the jaw or teeth
- Full dentures
- Braces
- Diagnosis of sleep apnea
- Less than 18 years of age

## Vulnerable Subjects

No vulnerable subjects will be recruited for this study.

## Methods and Procedures

## Methods and Procedures

Subjects who are interested in reducing their snoring will be recruited online. In order to participate in the trial, they will complete a pre-trial questionnaire, as well as review and sign the Informed Consent.

Assuming they satisfy the Inclusion and Exclusion criteria and sign the Informed Consent (includes the inclusion/exclusion criteria), they will purchase the device for \$90. The intraoral device and patient instructions will be mailed to them (Attachment E).

Once the subject is able to participate in the study, the device is placed in boiling water to soften it. While still warm, the device is placed in the mouth and molded to the individual patient. This is the same procedure used with many intraoral mouthpieces and devices including the Zyppah Boil and Bite.

The subject will be asked to use the intraoral device each night for ten consecutive nights. After they have used the device for ten days, a follow-up survey will be emailed to the subject. The patient will respond to the questions in the survey. After they have completed the follow-up survey and returned it, the subject will receive a full refund for the cost of the device (\$90). This is intended to increase compliance with the protocol.

This study will also evaluate the response of subjects who are at high risk of obstructive sleep apnea. The product instructions will contain a brief questionnaire (Attachment D, STOP-BANG Survey) assessing the subject's risk for OSA. If they are determined to be high-risk by the self-administered questionnaire, they will be given the following options: 1) complete a full, overnight in-office sleep study, 2) complete a discounted in-home sleep study, or 3) discontinue use of the device and return it for a full refund. The response of these subjects will be monitored to see how they respond and whether they continue to use the device or seek medical attention to evaluate their risk of sleep apnea.

This is a non-significant risk study, and the only 'extra' requirements for this study are the completion of the pre-study and post-study questionnaires by the patient.

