## II. Purpose and Background

The purpose of this study is to evaluate the safety and efficacy of an over-the-counter (OTC) intraoral mouthpiece to reduce snoring. A secondary objective is to evaluate the behavior of patients at high risk for sleep apnea to determine whether they will seek a conclusive diagnosis with a sleep study.

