# Background

Snoring is a common condition which negatively affects the quality of sleep for both snorers and their partners. It is estimated that nearly 30% of men and 9% of women suffer from habitual snoring, with risk factors including obesity, age (>40), smoking, and alcohol consumption. (Kara CO et al, *The prevalence of snoring in the adult population*, Kulak Buran Bogaz Ihtis, 2005, 14(1-2), 18-24).

Poor sleep quality has been shown to be a health risk for many conditions, including heart disease and hypertension, obesity, diabetes, mood disorders, reduces immune response and many others (http://healthysleep.med.harvard.edu/healthy/matters/consequences/sleep-and-disease-risk)

Snoring is often caused by a narrowing of the airway. As air is forced through this narrow passage it vibrates the skin of the airway, causing the distinctive sound of snoring. It is well established that slight changes in the positioning of the mouth, teeth, or tongue can significantly affect snoring.

This study is evaluating the safety and efficacy of an intraoral mouthpiece to reduce snoring. A similar intraoral mouthpiece, Zyppah Boil and Bite, is prescribed on the internet to more than 100,000 people every year. It is cleared under K111680.

The mouthpiece tested in this clinical trial is being evaluated as an over-the-counter product. It has the same features, except it does not move the lower jaw forward. The mouthpiece is designed to change the position of the mouth, and thereby increase the capacity of the airway. It also has a silicon strap placed over the tongue to stabilize it and open the airway. The mouthpiece is placed in boiling water to soften the plastic and then inserted in the mouth, customizing the shape for each user.

One concern in providing an OTC intraoral mouthpiece is the belief that a device intended to reduce snoring cannot reduce snoring associated with obstructive sleep apnea (OSA) and may cause patients not to enroll in a sleep study to diagnose (OSA). However, it is estimated by the American Sleep Apnea Association that 80% of moderate and severe sleep apnea remains undiagnosed. Our theory is that most patients are not making appointments for sleep studies to diagnose their sleep apnea, but are willing to buy an OTC mouthpiece to improve their snoring.

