## Obstructive Sleep Apnea (OSA)

Obstructive Sleep Apnea (OSA) is a sleep disorder where breathing stops and restarts multiple times during the night, interrupting sleep and often abruptly awakening the patient with a feeling of suffocation. There is significant overlap between snoring and patients with obstructive sleep apnea, which is estimated to affect 3-7% of men and 2-5% of women (Punjabi NM, *The Epidemiology of Adult Obstructive Sleep Apnea*, Proceedings of American Thoracic Society, 5:2, 2008).

The vast majority of those with sleep apnea also habitually snore, though the majority of habitual snorers *do not* have sleep apnea. From prevalence estimates, approximately 10% of male and 22% of female snorers may also have OSA. Women are eight times more likely to have their OSA undiagnosed than men.

The instructions for use of the mouthpiece helps the patient assess their risk of mild, moderate or severe OSA and may encourage them to register for an inexpensive home sleep study. It is hoped that this device may help some habitual snorers identify their risk of OSA and seek treatment. This clinical trial will also monitor the behavior of these users, looking to see whether they i) seek a sleep study, ii) return the device for a refund or iii) decide to use the snoring device. In the first two cases, they will be dropped from the clinical trial.

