#### Study Design

Patients will enroll in the study online. The on-line experience has been carefully designed to mimic the experience of buying the device in a retail store or on a website without consulting a sleep professional or dentist. After filling out a short online questionnaire to determine their initial symptoms and signing the informed consent, the product and instructions will be shipped to them. The device is used for a period of 10 days in the clinical trial. An email prompting them to complete a follow-up questionnaire will be sent ten days after the device has been received. Upon completion of the follow-up survey, the cost of the device will be refunded to the patient, incentivizing completion of the study.

The surveys will ask the patients to qualitatively and quantitatively compare their snoring before use of the device and after 10 days of using the device.

As part of the follow-up survey, users will be asked if they self-identified (on the basis of the product instructions) as being at risk for OSA. If they answer positively, they will be asked about their response, including whether they sought medical care, enrolled in a sleep study, or discontinued use of the device.

A two-sample t-test will be used to analyze the change from the initial survey to the follow-up survey, with patients serving as their own controls.

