# Payment for Participation

No payments will be given for participation, other than providing the study device at no cost (should the subject complete the trial).

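### Returns, continued use and sleep-study uptake among high-risk subjects are observed with a free device and a discounted home study, so they cannot be read as the behavior of paying over-the-counter buyers

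*Combined protocol and SAP*

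**What the plan says.** II. Purpose and Background sets the question: "A secondary objective is to evaluate the behavior of patients at high risk for sleep apnea to determine whether they will seek a conclusive diagnosis". Background gives the reason, a worry that a snoring device sold without supervision could keep people with apnea from being tested. It answers with the sponsor's theory that "most patients are not making appointments for sleep studies to diagnose their sleep apnea, but are willing to buy an OTC mouthpiece". The section on Obstructive Sleep Apnea (OSA) names the behaviors to be watched, namely whether users "i) seek a sleep study, ii) return the device for a refund or iii) decide to use the snoring device", and says that users in the first two groups leave the trial.

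Study Design stresses realism: "The on-line experience has been carefully designed to mimic the experience of buying the device in a retail store or on a website". The follow-up survey asks subjects who saw themselves as at risk what they did, including "whether they sought medical care, enrolled in a sleep study, or discontinued use of the device".

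Methods and Procedures gives high-risk subjects three options: an overnight in-office study, or "2) complete a discounted in-home sleep study, or 3) discontinue use of the device and return it for a full refund".

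The money terms are spread over several sections. The subject pays $90 at enrollment. Study Design, Methods and Procedures, and Costs to the Subject all return that sum after the follow-up survey, and all present it as a means of getting the study completed. Without the survey there is no refund. Payment for Participation sums this up: "No payments will be given for participation, other than providing the study device at no cost (should the subject complete the trial". Transition from Research Participation expects subjects to go on using the device afterwards.

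**The concern.** The secondary result is meant to bear on whether over-the-counter sale deters diagnosis of apnea. Two terms act on the behaviors being counted.

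- **The survey refund.** It makes the device free to anyone who keeps it and answers the survey, so the choice between keeping and returning is not the one a paying buyer faces.
- **The discounted home study.** It may raise uptake. If the discount will not come with the marketed product, the observed uptake is not what retail buyers would show.

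The plan gives no comparator, benchmark rate or analysis method for this objective, and it does not discuss how these terms limit the reading of the result. If the route to a sleep study is not recorded while the trial runs, it may not be recoverable later.

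**Working it through.** **The plan's only sample-size figure.** Data Analysis and Monitoring: 350 completers at 30% dropout gives 350 / (1 − 0.30) = 500, which reproduces. It concerns the primary endpoint only, and nothing below depends on it being right.

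**Step 1: net cost of each choice.** The trial rows use the documents' own $90 terms. The buyer rows assume the same price, no survey refund, and returns refunded in full.

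| Choice | Paid | Refunded | Net cost | Has device |
|---|---|---|---|---|
| Trial: keep, complete survey | $90 | $90 | $0 | yes |
| Trial: return for refund | $90 | $90 | $0 | no |
| Trial: keep, no survey | $90 | $0 | $90 | yes |
| Buyer: keep | $90 | $0 | $90 | yes |
| Buyer: return | $90 | $90 | $0 | no |

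Gain from returning: for a buyer, $90 − $0 = $90; for a trial subject who would complete the survey, $0 − $0 = $0. The money term on its own favors keeping. How many subjects it sways cannot be computed, because the documents give no return rate.

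**Step 2: what the route item would show.** The documents give no discount size, study price or uptake rate, so these inputs are assumed: 30% of 350 at high risk, 0.30 × 350 = 105; 8 arrange a study themselves; 12 use the discount.

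- All routes: (8 + 12) / 105 = 20/105 = 19.0%.
- Excluding discount users: 8/105 = 7.6%.

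The second figure is not the rate that would have been seen with no discount, since some of the 12 might have arranged a study anyway. If the discount only adds or diverts studies, the no-discount rate lies between 7.6% and 19.0%. If nobody uses the discount, the two bounds coincide. They concern the discount alone; the refund terms act on both.

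**Step 3: who is observed.** The OSA section drops sleep-study seekers and returners, while Study Design relies on the follow-up survey to learn of those same actions. Data Collection places STOP-BANG (Attachment D) in the post-questionnaire and not in the pre-questionnaire. If dropped subjects are not surveyed, the trial may lack both their action and their risk score. On the Step 2 figures, losing all 20 would leave 0 of 85 (105 − 20), or 0%.

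Whether a dropped sleep-study seeker still receives the survey refund is not stated. If not, seeking diagnosis could forfeit $90 and push uptake down, against the pull of the discount. The net direction for uptake is therefore not established.

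**Step 4: precision.** If 10% to 40% of 350 are at high risk (assumed; n = 35 to 140), the 95% half-width around 20% uptake is 1.96 × √(0.20 × 0.80 / n), or 13.3 to 6.6 points. A larger sample would narrow this but would not remove a shift caused by the terms.

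**The case against.** The strongest reply is that the home-study offer belongs to the product. The OSA section says the instructions for use may point users to a low-cost home study. Methods and Procedures introduces the three options right after saying that the instructions contain the risk questionnaire, and it describes the two questionnaires as the only added burden of the trial. If so, the effect of the discount is part of what the sponsor wants to observe. This stands as a real possibility, and a reader should not infer that the discount is a trial-only subsidy. But no section says that the same discount will accompany the marketed device.

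A reader might also infer that the survey pools all sleep studies into one answer. The documents do not show that. Study Design gives a non-exhaustive list of topics, and the survey wording is not available. What can be said is that the described content does not mention the route.

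A third tempting inference is that returning is never the better choice. In money it is no better than keeping, but keeping at $0 requires completing the survey, while the return option states no such condition. For someone who does not want the device, returning may take less effort.

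Finally, the retail comparison in Study Design goes on to stress the absence of professional advice, not price, and no section promises to report a retail return rate. That is fair. Background still frames the question as one about over-the-counter sale, so a reader will take the rates that way unless told otherwise.

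**Conclusion.** The point holds as a limit on interpreting a secondary, descriptive result. The refund leg is firm: by the plan's own account the survey refund is a completion incentive, and it removes the $90 gain from returning. Return and continued-use rates therefore cannot be read as those of paying buyers. The discount leg is conditional on whether the discount will come with the marketed product, which the documents leave open.

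It would go too far to say that the secondary result is produced by the trial's terms, or that uptake is inflated. Neither the size nor the net direction of any shift can be derived, and the 7.6% to 19.0% range rests wholly on assumed counts. The sample size, significance level, power and primary endpoints are untouched. This is a cheap improvement, worth making because the missing information may not be recoverable afterwards.

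**What to change.** 1. For every high-risk subject, record the route to a sleep study (in-office, discounted home study, arranged otherwise, none) together with return and refund status. Include subjects dropped under the OSA section, with their STOP-BANG result. Reconcile that section with the follow-up survey in Study Design, and state whether dropped subjects are surveyed and receive the survey refund. Also reconcile its list of behaviors, which includes continued use, with the options in Methods and Procedures, which do not.
2. Report the rate for each route and the total, over all high-risk subjects. Unless the same discount will accompany the marketed product, present the rate excluding discount users as a lower bound and the total as an upper bound, stating the assumption that the discount only adds or diverts studies. Do not present the lower figure as the no-discount rate.
3. Do not present return or continued-use rates as retail behavior, and state that the device was free to survey completers.

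Cost: one added survey item, follow-up of dropped subjects, and a few sentences in the report. The downside is a headline uptake figure that may be less favorable or come as a wider range.

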# Data Collection

- Attachment A is the list of questions to gather personal information about the subject, including age, gender, weight, height and contact information. This will allow for the calculation of Body Mass Index (BMI), a well-known risk factor in both snoring and obstructive sleep apnea. This attachment also contains the Inclusion/Exclusion criteria, where potential subjects will be asked to review and certify that they meet the requirements of the trial (they will also see this information later in the process at the Informed Consent).
- Attachment B is the Visual-Analog Scale (VAS) asking potential subjects how much their snoring is bothering them and their partner (if applicable). The VAS method is commonly used and has been validated for patient satisfaction (Brokelman et al, 2012).
- Attachment C is the Snoring Severity Scale (SSS). This validated, three-question survey has been shown to accurately assess the severity of snoring and the risk for obstructive sleep apnea (Morris L et al, 2008)
- Attachment D is the Stop-Bang Assessment, which is the most frequent assessment used to determine the risk of sleep apnea. This 8-question survey has been validated as a risk assessment for moderate to severe sleep apnea (Nagappa et al, 2015).

The pre-questionnaire will consist of Attachments A, B, and C to establish a baseline. The postquestionnaire will consist of Attachments B, C, and D, also allowing the study to evaluate the response of subjects at high risk of OSA.

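### No described question separates sleep studies sought after the product instructions from studies already done or booked beforehand

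*Combined protocol and SAP*

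**What the plan says.** In the combined protocol and SAP, Purpose and Background sets a secondary objective in these words: "evaluate the behavior of patients at high risk for sleep apnea to determine whether they will seek a conclusive diagnosis with a sleep study". The reasoning behind it is given under Background: "Our theory is that most patients are not making appointments for sleep studies to diagnose their sleep apnea".

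Data Collection lists the baseline instruments: "The pre-questionnaire will consist of Attachments A, B, and C to establish a baseline". Attachment A "is the list of questions to gather personal information about the subject, including age, gender, weight, height and contact information", and it also carries the eligibility certification. Attachment B is a VAS on how bothersome the snoring is. Attachment C is the Snoring Severity Scale, described thus: "This validated, three-question survey has been shown to accurately assess the severity of snoring and the risk for obstructive sleep apnea". The post-questionnaire repeats B and C and adds D, the STOP-BANG assessment.

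The only exclusion that concerns sleep is "Diagnosis of sleep apnea". The section on Obstructive Sleep Apnea says the trial will look at "whether they i) seek a sleep study, ii) return the device for a refund or iii) decide to use the snoring device". Study Design adds that, at follow-up, subjects who judged themselves at risk from the product instructions are asked what they did about it, enrolling in a sleep study being one of the answers.

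**The concern.** The objective is about behavior after the subject learns of the risk. To measure that, one must know who had already been tested, or already had an appointment, before the instructions arrived. The trial has no control group, so a baseline question is the only internal reference.

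Two kinds of eligible high-risk subject cause difficulty. One had a sleep study that did not find sleep apnea, may see little reason to repeat it, and can be counted as not seeking. The other had booked a study before enrolling and can be counted as having responded to the STOP-BANG result and instructions. Neither is removed by the exclusion criteria, and neither has a place among the three monitored behaviors. If this history is not collected, it cannot be recovered at analysis. The result bears on a concern that Background itself raises, namely that an over-the-counter device might keep users away from a sleep study.

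**Working it through.** **The plan's own figure.** The only sizing figure is 350 / (1 - 0.30) = 500 enrolled, which reproduces. It concerns the VAS endpoint. No target, precision or sample size is stated for the proportion seeking a sleep study, so this point has no planned figure to recompute.

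**Where the information could be captured.**

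| Place | Earlier or booked sleep study described? |
|---|---|
| Attachment A (personal data, eligibility) | No, but the list of contents is not exhaustive |
| Attachment B (VAS) | No |
| Attachment C (Snoring Severity Scale) | No |
| Attachment D (STOP-BANG, post-questionnaire) | No |
| Exclusion criteria | Only a diagnosis already made |
| Follow-up question in Study Design | Asks about the response to the risk; no date or before/after item described |

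**Possible size (all rates assumed).** Among high-risk subjects let a be the share with a prior negative study, b the share already booked, and s the new-seeking rate among the rest. Suppose no previously tested subject seeks another study and every earlier booking is reported. Then

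reported rate = (1 - a - b) × s + b, and error = reported - s = b × (1 - s) - a × s.

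| s | a | b | Reported | Error (points) |
|---|---|---|---|---|
| 10% | 0 | 5% | 14.5% | +4.5 |
| 10% | 0 | 10% | 19% | +9 |
| 10% | 10% | 0 | 9% | -1 |
| 10% | 20% | 0 | 8% | -2 |
| 20% | 0 | 5% | 24% | +4 |
| 20% | 20% | 0 | 16% | -4 |
| 20% | 20% | 5% | 20% | 0 |

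The two errors act in opposite directions and cancel when b × (1 - s) = a × s. In the last row, 0.05 × 0.80 = 0.20 × 0.20 = 0.04.

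**The same in counts, for an assumed 100 high-risk subjects.**

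- 5 already booked, 10 with a prior negative study, 10 of the other 85 newly seeking. Reported with bookings included: 15/100 = 15%. Actions begun after the instructions: 10/100 = 10%. Among those with no study and none planned: 10/85 = 11.8%.
- None booked, 20 with a prior negative study, 10 of the other 80 newly seeking. Reported: 10/100 = 10%. Actions begun after the instructions: also 10/100. Among those with no study and none planned: 10/80 = 12.5%.

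A timing rule thus removes the booking error from the overall proportion. The effect of prior negative studies shows only in a breakdown by baseline category.

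**Against sampling error.** At n = 100 the 95% half-width is 1.96 × sqrt(0.15 × 0.85 / 100) = 7.0 points at 15%, and 1.96 × sqrt(0.10 × 0.90 / 100) = 5.9 points at 10%. The differences between the reported and the subgroup rate in these two examples (15 - 11.8 = 3.2 and 12.5 - 10 = 2.5 points) are smaller than that.

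**The case against.** The strongest reply is that the gap is one of description. Attachment A is not reproduced and its contents are given as examples. The follow-up behavior questions in Study Design also do not appear in the descriptions of B, C or D, so Data Collection is a summary and not an item list. This stands: a reader might infer that the trial fails to record sleep-study history, but the documents show only that no such item is described.

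Second, no counting rule is stated, so a reader might infer that earlier bookings will be scored as responses, but that does not follow. The follow-up asks for the response of people who recognized their risk from the instructions, and some would leave out a booking made before then. This covers part of the booking problem, but it leaves the decision to each respondent. It also does nothing for prior negative studies.

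Third, a reader might conclude that the secondary result can neither support nor refute the theory in Background. That goes too far. In both count examples most subjects do not seek a study under either calculation, so the reading of the theory does not change.

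Fourth, restricting the main result to people with no study and none planned would remove those already booked, who are evidence against the sponsor's theory. In the first example the figure falls from 15% to 11.8%, in the theory's favor. This objection stands and shapes the fix.

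Finally, Study Design says enrollment is meant to resemble a retail purchase, and a sleep-study question before purchase could prompt the behavior being measured. The cost is real but modest, because the sleep apnea exclusion is already shown at that stage.

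**Conclusion.** The point holds in limited form. No described instrument records whether a subject had, or had booked, a sleep study before receiving the instructions, and eligibility screens out only a diagnosis. The secondary result therefore cannot reliably separate new seeking from earlier studies or bookings.

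Size and net direction are unknown. The range of -4 to +9 points rests wholly on assumed rates (s of 10% or 20%, a up to 20%, b up to 10%) and on full misclassification of both groups. Any response measured is to the STOP-BANG result and instructions, so it should not be read as a response to wearing the device. The primary VAS and Snoring Severity Scale analysis and the 350/500 sizing do not depend on this. It is a cheap improvement to a descriptive secondary objective.

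**What to change.** - Unless Attachment A already contains it, add one item beside the existing sleep apnea exclusion with three answers: no sleep study and none planned; one already booked; had one and sleep apnea was not found. If the item exists, cite it in Data Collection.
- In the follow-up question, ask whether any sleep study was arranged before or after the instructions were received.
- Keep the proportion among all high-risk subjects as the secondary result, and count as newly seeking only actions begun after the instructions.
- Report the result by the three baseline categories, including the proportion among those with no study and none planned.

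The cost is one extra question before purchase with slight priming, one added follow-up question, a sentence or two in the analysis section, and a smaller denominator for the subgroup figure.

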# Data Analysis and Monitoring

The primary endpoints, a VAS assessment of snoring and the Snoring Severity Scale will be analyzed using a two-sample *t*-test comparing the pre-study and post-study questionnaire results. The ANCOVA method may also be used to evaluate the impact of different variables, like age, weight, gender, or others, on the study results. There are no potential serious risks to patients, and no stopping criteria that need to be analyzed during the study.

In determining sample size, it was estimated that the device would produce a 15% improvement in snoring, as measured on the VAS. With a level of significance of p < 0.05 and a power of 80%, approximately 350 subjects will need to complete the study to generate statistically significant data. Assuming a 30% dropout rate for non-compliance with the study or the discovery of moderate to severe sleep apnea, 500 subjects will be enrolled in the study to ensure the study is adequately powered.

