## Data Storage and Confidentiality

Data will be collected via a password-protected website and confidential email forms. The results will be securely stored in password-protected cloud storage and then downloaded onto a personal computer to be compiled in Excel. Once transferred to Excel, the data will also be placed into a password-protected file. This data will be available to the study coordinator alone, as the principal investigator is blinded (a precaution since he has a financial interest in the device). Subject identifiers will be necessary, but only the study coordinator will have access to the data with subject identifiers. These identifiers will be removed before any data or statistical analysis is conducted. The principal investigator will be provided the subject identifier and data for any patient that has an unexpected serious reaction to use of the device for analysis and response as well as notification of regulatory bodies and the investigational review board.

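### Safety is half of the stated purpose, but the plan names no safety endpoint or analysis, and the follow-up survey as described asks nothing about harm of all subjects

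*Combined protocol and SAP*

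**What the plan says.** The opening sentence of Purpose and Background reads "The purpose of this study is to evaluate the safety and efficacy" of the mouthpiece; the sleep apnea behaviour objective is secondary.

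- **Endpoints and analysis.** Data Analysis and Monitoring says "The primary endpoints, a VAS assessment of snoring and the Snoring Severity Scale will be analyzed", by a pre/post *t*-test with an optional ANCOVA. Statistical Analysis repeats the pre/post questionnaire comparison. Neither section mentions safety data.
- **Follow-up data.** Data Collection says "The postquestionnaire will consist of Attachments B, C, and D" (VAS, Snoring Severity Scale, STOP-BANG). Study Design adds that subjects who judge themselves at risk of sleep apnea are asked how they responded, "including whether they sought medical care, enrolled in a sleep study, or discontinued use of the device".
- **Other procedures.** Methods and Procedures says the only extra requirements "are the completion of the pre-study and post-study questionnaires by the patient".
- **Routes for harms.** Data Storage and Confidentiality sends to the principal investigator the data of "any patient that has an unexpected serious reaction to use of the device". Potential Risks directs subjects to customer service if a correct fit cannot be obtained and tooth soreness persists. Costs to the Subject has the sponsor pay uninsured complication costs.
- **Who is followed.** Under Obstructive Sleep Apnea, at-risk users may seek a sleep study, return the device or use it; "In the first two cases, they will be dropped from the clinical trial". Study Design sends the survey email ten days after the device is received, whereas Methods and Procedures sends it after ten days of use.

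**The concern.** The plan foresees specific harms: burns from a hot mold, detachment of the strap, damage to fillings or crowns, and mouth or tooth soreness. Following it as described would still give no proportion of users who had any of them. Soreness that settles after re-molding has no described route into the data at all.

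A low number of reports could then mean few harms or few reports, and the study could not tell these apart. Half of the stated purpose would go unanswered for the non-serious harms that the plan itself lists. Experiences over ten nights that nobody asked about are hard to recover later. Subjects who stop early or are dropped may be the ones with something to report, and on one reading of the survey trigger they may not be contacted.

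**Working it through.** **1. Purpose set against plan.**

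| Element | Efficacy | Safety |
|---|---|---|
| Named in the purpose | Yes | Yes |
| Endpoint | VAS and Snoring Severity Scale | None named |
| Survey item for all subjects | VAS and Snoring Severity Scale | None described |
| Planned analysis | Pre/post *t*-test, optional ANCOVA | None |
| Other route | Not needed | Serious-reaction escalation (no detection method stated), customer service, complication costs |

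**2. The plan's own figure.** Data Analysis and Monitoring gives about 350 completers and 30% dropout: 350 / (1 − 0.30) = 500, so the enrolment figure reproduces. The inputs to the sample size concern the VAS; none concerns safety.

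**3. What 350 answers to a harm question would give.** All figures are exact binomial with n = 350.

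- Zero events, one-sided 95% upper bound: 1 − 0.05^(1/350) = 0.85%. The two-sided 95% upper limit is 1 − 0.025^(1/350) = 1.05%.
- 7 events: 7/350 = 2.0%, Clopper-Pearson 95% CI 0.8% to 4.1%.
- 35 events: 35/350 = 10.0%, Clopper-Pearson 95% CI 7.1% to 13.6%.
- Chance of seeing at least one case of an event with a true rate of 1%: 1 − 0.99^350 = 97.0%.

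The event counts are illustrations. The documents give no frequency for any of these harms.

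**4. What loss to follow-up does.** The intervals in step 3 cover respondents only. With 500 − 350 = 150 recipients unobserved, the proportion among all 500 can lie anywhere between the cases where none and all of the 150 had the event:

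- 35 reports: 35/500 = 7% to (35 + 150)/500 = 37%.
- Zero reports: 0/500 = 0% to 150/500 = 30%.

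Who is reached therefore matters more than sampling error.

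**5. Who is reached.** With the email timed from receipt, a subject who stops on night three still gets the survey. With the email timed from ten days of use, that subject may not. The Study Design questions on sleep studies and stopping use imply that some subjects counted as dropped still answer, but the plan does not secure this.

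**The case against.** The strongest objection is that the attachments, consent pages and product instructions are not shown. The listing of Attachments B, C and D is also not the full content of the survey, because Study Design adds questions. The recruitment notice allows about 10 minutes for the post-study survey against 5 for the pre-study one. A harm item could therefore exist. This stands, and it makes the point about ascertainment conditional. It does not reach the missing endpoint and analysis, which rest on text that is fully visible.

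Second, harm reporting is not absent. A reader might infer that the plan has no safety reporting, or that every route is purely spontaneous. The documents support neither: serious reactions are escalated and regulators and the review board notified, and how such reactions or complication costs come to notice is simply not stated. None of these routes, however, is described as asking every subject.

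Third, the study is described as minimal risk, with more than 100,000 users of the marketed product and no known loss of a filling or crown. Minimal risk bears on oversight and does not answer a stated safety purpose. Prior use is relevant but gives no soreness frequency. The documents also differ on what was used: Background calls the marketed product similar and says of the tested one "It has the same features, except it does not move the lower jaw forward", while Risk Category says this device itself has been marketed for another application. That difference should not be pressed as added danger, since Potential Risks takes the absence of jaw advancement to remove jaw and bite risks.

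**Conclusion.** The point holds and should be settled before data are collected. Safety is a stated purpose with no named endpoint and no planned analysis. As the survey is described, no item asks all subjects about harm. Unless an attachment already does so, the trial cannot report a harm proportion among subjects who were asked.

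Two further inferences should be resisted. One is that these harms are common and would be heavily under-counted: the plan says only that soreness can result, and it gives neither a rate nor a reporting fraction, so the size of any under-count cannot be estimated. The other is that 350 answers would bound the risk for all users at 0.85%. That bound applies to respondents, assumes zero events and 350 of them, and says nothing about the 150 expected to be lost.

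**What to change.** 1. **Survey.** Add a short harm checklist for every device recipient to the existing follow-up survey: heat injury, strap detachment, damage to a filling, crown or tooth, mouth or tooth soreness (including soreness that resolved), and other. For each, ask severity and whether use stopped. Also ask whether the device was used and for how many nights.
2. **Timing and reach.** Reconcile the two survey triggers so that the safety items go out by time since receipt. Include subjects who stop early and those dropped after seeking a sleep study or returning the device. This need not change who enters the efficacy analysis.
3. **Endpoint and analysis.** Name as a descriptive safety endpoint the proportion with each event among respondents who used the device, with exact 95% confidence intervals. Report the number of recipients who did not respond.

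If the attachments already hold a harm item, only the endpoint, the analysis and the contact of early stoppers and dropped subjects need adding.

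The cost is a slightly longer survey (check the 10-minute statement in the recruitment notice), an email to recipients not otherwise reached, and one table. No visits or subjects are added. Without a control group the rates stay descriptive, and a checklist will pick up some complaints unrelated to the device.
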